3 STATISTICAL METHODOLOGY

3.1 General Considerations

3.1.1 *Analysis Day*

Analysis days will be calculated from the date of starting infusion of study drug. The day on which infusion of study drug is started is Day 1, and the day immediately before Day 1 is Day -1. For the purpose of this statistical analysis there is no Day 0.

3.1.2 *Analysis Visits*

Scheduled visits will be assigned to analysis visits as recorded on the case report form (CRF). Unscheduled and early termination visits will be assigned to analysis visits according to the analysis windows in Table 5. The record occurring on the target day will be picked for the time point analysis. If the record on a target day does not exist, then the one closest to the target date will be used.

Table 5. Analysis windows

| Analysis Visit | Target Analysis Day | Low Analysis Day | High Analysis Day |
|----------------|---------------------|------------------|-------------------|
| Baseline | -1 | | -1 |
| DAY 1 | 1 | 1 | 1 |
| DAY 2 | 2 | 2 | 3 |
| DAY 6 | 6 | 4 | 8 |
| DAY 30 | 30 | 9 | 44 |
| DAY 90 | 90 | 45 | 104 |

3.1.3 *Definition of Baseline*

Baseline is defined as the last measurement prior to start of the study drug infusion. Baseline blood work, ECG and CXR (Day 1) are not required prior to randomization or start of study drug infusion. Baseline infarct volume indicates the initial infarct volume as obtained from the first MRI approximately 2 hours post-endovascular thrombectomy on Day 1.

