2.2 Study Design

2.2.1 Overview

This trial is a Phase 2, block urn randomized, blinded assessor, placebo-controlled, parallel group, two-dose (high and low), and longitudinal (pre-stroke, post-treatment, 48-hour, discharge, and Days 30 and 90) study with equal arm sample sizes (1:1:1). All participants in the trial will be followed for 90 days (or until death if prior to 90 days). Participants are considered to have completed the study if they have remained in the study until Day 90 or they have died prior to Day 90. The end of the trial is defined as the date the last enrolled participant has completed their Day 90 visit/contact.

The trial's primary aim is to demonstrate the safety of RNS60. As a secondary aim, the study will provide first data on whether RNS60 may reduce global disability, improve neurological outcome, reduce worsening of stroke and reduce infarction volumes. Superiority of the higher dose is hypothesized over placebo and of the lower dose over placebo is hypothesized for all secondary and tertiary objectives.

AIS large vessel occlusion participants who are selected for Endovascular Thrombectomy (EVT) will be given a 48-h infusion of either 0.5 mL/kg/h RNS60 (up to a maximum of 65 mL/h), 1.0 mL/kg/h RNS60 (up to a maximum of 130 mL/h), or 1.0 mL/kg/h (up to a maximum of 130 mL/h) placebo (normal saline) starting within 30 minutes of randomization (but prior to arterial access closure).

Randomization will be done with block urn randomization to balance age (<80 vs. \geq 80), NIHSS score (6-10 vs. >10), and Alberta stroke program early computerized tomography score (ASPECTS) (5-7 vs. 8-10) for a total of 8 urns.

Table 1 shows the schedule of activities of randomized participants.

Table 1: Schedule of Activities for Randomized Participants

| Visit/Contact | V1 | V2 | V3 | V4 | V5 | V6/ End of Trial |
|---|---------------------|-------------------|--------------------------------|------------------------------------|---------------------|---------------------|
| Day | Day 0 Baseline | Day 1 Post-EVT | Day 2/or early discharge | Day 6 ¹ or discharge | Day 30 ² | Day 90 ² |
| Window | (24 h+/-4h) | | (48 h+4h) | (-5 d) | | (-21 to +7d) |
| Informed consent | X | | | | | |
| Regained capacity informed consent ³ | | | X | X | X | X |
| History and physical examination ⁴ | X | X | X | | | |
| Weight ⁵ | X | | X | | | |
| Vital Signs (BP, HR, Temperature) ⁶ | X | X | X | | | |
| Chest radiograph | X ¹² | X | X | | | |

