The NIHSS is a standardized neurological examination scale that is a valid and reliable measure of disability and recovery after acute stroke. The NIHSS assessment is a standardized 15-item impairment scale, intended to evaluate neurologic outcome and degrees of recovery for subjects with stroke. The scale assesses levels of consciousness, extraocular movements, visual fields, facial muscle function, extremity strength, sensory function, coordination (ataxia), language (aphasia), speech (dysarthria), and hemi-inattention (neglect). The NIHSS will be administered at baseline, post-EVT (2h), 24h, 48h, Day 6 (or discharge), Day 30 and Day 90. The NIHSS will only be scored by those trained in the use of this scale.

Table 3. Scales and score range in NIHSS

| Item | Scales | Score range |
|------|----------------------------|-------------|
| 1a | Level of Consciousness | 0-3 |
| 1b | LOC Questions | 0-2 |
| 1c | LOC Commands | 0-2 |
| 2 | Best Gaze | 0-2 |
| 3 | Visual | 0-3 |
| 4 | Facial Palsy | 0-3 |
| 5a | Motor Arm –Left Arm | 0-4 |
| 5b | Motor Arm –Right Arm | 0-4 |
| 6a | Motor Leg –Left Leg | 0-4 |
| 6b | Motor Leg – Right Leg | 0-4 |
| 7 | Limb Ataxia | 0-2 |
| 8 | Sensory | 0-2 |
| 9 | Best Language | 0-3 |
| 10 | Dysarthria | 0-2 |
| 11 | Extinction and Inattention | 0-2 |

Scoring:

Each item is scored in the respective ranges listed in Table 3 (0-2, 0-3, or 0-4), and untestable items are scored as "UN". A score of 0 indicates normal performance. Total scores on the NIHSS range from 0-42, with higher values reflecting increasing severity.

Stroke severity is further stratified in the following way (Brott, Adams, Olinger, Marler, Barsan, Biller, & Hertzberg, 1989):

> 25: Very severe

15-24: Severe

5-14: Mild to moderately severe

< 5: Mild

The predictive value of the scale can also aid in planning a subject's rehabilitation or long-term care needs as early as on the day of admission. NIHSS scores can be

interpreted in the following way (Schlegel, D., Kolb, S. J., Luciano, J. M., Tovar, J. M., Cucchiara, B. L., Liebeskind, D. S., & Kasner S. E., 2003):

≥ 14 – Severe: Long-term care in nursing facility required

6-13 – adequate: Acute inpatient rehabilitation required

≤ 5 – Mild: 80% with this score are discharged home

4) The proportion of study subjects with worsening of stroke at the 90-day study period.

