3.1.6 Handling of Dropouts and Missing Data

For participants who have missing observations on 90-day mRS, 24-hour NIHSS, worsening stroke, or infarct volume, the missing data in the primary analyses will be managed with an assumption of MAR using longitudinal mixed models. In addition, every effort will be made to complete assessments using the participants legally authorized representative (LAR) for information if needed. Assessments with missing elements will be considered missing as a whole. Missing dates will be queried at the site level prior to database lock.

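### The Baseline, DAY 1 and DAY 2 rows of SAP Table 5 do not fit the day count in SAP 3.1.1, so an unscheduled or early-termination record at 24 h is filed as DAY 2, not DAY 1

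*SAP*

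**What the plan says.** SAP 3.1.1 counts analysis days by calendar date from the start of infusion: "The day on which infusion of study drug is started is Day 1, and the day immediately before Day 1 is Day -1". It adds that Day 0 does not exist for the analysis.

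SAP 3.1.2 separates two kinds of record. Scheduled visits take the visit recorded on the CRF. For the rest, "Unscheduled and early termination visits will be assigned to analysis visits according to the analysis windows in Table 5". Within a visit, "The record occurring on the target day will be picked for the time point analysis"; failing that, the closest record is used. The early rows of Table 5 are:

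- Baseline: target Day -1, upper limit Day -1
- DAY 1: target 1, window 1 to 1
- DAY 2: target 2, window 2 to 3
- DAY 6: target 6, window 4 to 8

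SAP 3.1.3 defines baseline by time, not date: "Baseline is defined as the last measurement prior to start of the study drug infusion".

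The schedule (SAP Table 1, Protocol Table 1-1) uses another count. Its first visits are "Day 0 Baseline | Day 1 Post-EVT", and randomization and start of study drug belong to the Day 0 visit. In Protocol Table 1-1 the Day 1 visit has a window of 24 h +/-4 h and the Day 2 visit 48 h +4 h. Footnote 8 of both tables gives the MRI its own times: about 2 h post-EVT on Day 1, and 48 h +/-4 h.

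**The concern.** Table 5 borrows its labels and target numbers from a schedule in which infusion starts on Day 0, but applies them to a count in which infusion starts on Day 1. The labels and the windows then describe different clock times. Both counts remain in use elsewhere: SAP 3.5.1 tabulates treatment-emergent events from Day 0 although 3.1.1 abolishes that day.

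Infarct volume at 48 h and NIHSS at 24 h rank second and third in the efficacy hierarchy of SAP 3.4.2. Suppose the scheduled 24-h NIHSS is missing but an unscheduled one was taken at 24 h. Table 5 does not let it serve as the DAY 1 value and makes it a DAY 2 value. If the scheduled 48-h value is also missing, the 24-h score can stand in for it as observed data. SAP 3.1.6 instead intends that for such gaps "the missing data in the primary analyses will be managed with an assumption of MAR using longitudinal mixed models". Safety summaries by time point are exposed in the same way. Protocol 8.1.2 calls for repeat ECGs after certain QTcF findings, so unscheduled ECG records on Days 1 to 3 are foreseeable.

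**Working it through.** The plan gives no figure to reproduce. The check applies the 3.1.1 count to records at known hours from infusion start.

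**Inputs.** Day count and windows: SAP 3.1.1 and Table 5. Visit times: Protocol Table 1-1 and footnote 8. S is the clock time of infusion start in hours (0 to <24) and T is hours from start. The documents do not give the distribution of S.

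**Formula.** On or after the infusion date, analysis day = 1 + floor((S + T)/24).

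**Results that hold for every start time**

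- T = 24: S + 24 lies in [24, 48), so the record is Day 2. It is outside DAY 1 (1 to 1) and on the DAY 2 target.
- T = 48: S + 48 lies in [48, 72), so the record is Day 3. It is inside DAY 2 (2 to 3) but one day off target. Among windowed records, a competing 24-h record on Day 2 is preferred to it.
- T from 20 to <24: the record stays on Day 1 only if S + T < 24. That requires a start before 04:00 at T = 20, and earlier still as T approaches 24.
- A pre-dose record on the infusion date is Day 1, so Table 5 files it as DAY 1 while 3.1.3 makes it baseline.

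**Shares, assuming S uniform over 24 h and T uniform over the visit window**

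- 24 h +/-4 h: Day 1 share = (1/8) x integral from 0 to 4 of (u/24) du = 1/24 = 4.2%. By symmetry Day 3 is 4.2%, and Day 2 is 22/24 = 91.7%. So 4.2% go to DAY 1 and 95.8% to DAY 2.
- 48-h MRI, 48 h +/-4 h: by the same integral, Day 2 is 4.2%, Day 3 is 91.7% and Day 4 is 4.2%. The Day 4 records are filed as DAY 6.
- Pre-dose record t hours before start: it shares the infusion date with probability 1 - t/24, which is 97.9% at 0.5 h and 89.6% at 2.5 h.

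**Range by start time**

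- All starts 08:00 to 20:00: 24 h +/-4 h gives S + T from 28 to 48, so all are Day 2. For the MRI, S + T runs from 52 to 72, so all are Day 3.
- All starts 18:00 to 24:00: every 24 h +/-4 h record is still in the DAY 2 row. The MRI share on Day 4 is (1/8) x integral from 0 to 4 of (u/6) du = 1/6 = 16.7%.

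**Later rows.** Schedule Days 6, 30 and 90 become analysis Days 7, 31 and 91. These lie inside 4 to 8, 9 to 44 and 45 to 104, so the one-day shift has negligible effect there.

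**The case against.** The strongest reply is that the rule has little to act on. The 24-h NIHSS and 48-h imaging are scheduled and keep their CRF visit. Early discharge is part of the scheduled Day 2 visit. Patients who stop study drug are followed to Day 90 (Protocol 7.1). Deaths are scored by rule for mRS, NIHSS and BI (SAP 3.1.7) and left missing for infarct volume (SAP 2.1.3). Early-termination records in the first three days would come mainly from withdrawal. All of this stands and limits the size of the point, but it does not make the rows consistent with 3.1.1.

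A reader might infer more than the documents support:

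- **That scheduled 24-h and 48-h endpoint data are misfiled.** They are not, because Table 5 does not place them.
- **That the NIHSS at 2 h post-EVT takes the place of the 24-h score.** It is a planned assessment: "The NIHSS will be administered at baseline, post-EVT (2h), 24h, 48h, Day 6 (or discharge), Day 30 and Day 90". How the CRF labels it cannot be seen, and the sample NIHSS form in Protocol 13.2 has separate boxes for 2 hours and 24 hours.
- **That the post-EVT MRI is misfiled.** The SAP itself puts that scan on Day 1 (Table 1 footnote 8 and 3.1.3), so DAY 1 is right for it.
- **That an unscheduled record on the target day displaces a scheduled one.** The target-day sentence follows directly on the windowing of unscheduled and early-termination visits and can be read as choosing only among those. The text does not settle it, and one sentence would.

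The shares can also be challenged: they borrow scheduled windows for records that are by definition unscheduled, and they assume the start times. Only the results at exactly 24 h and 48 h, and the conflict over baseline, are free of assumption.

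**Conclusion.** The point holds as a minor error in a stated rule, limited to unscheduled and early-termination records. On the 3.1.1 count, Table 5 cannot file a record at 24 h or later in the visit window as DAY 1. It prefers a 24-h record over a 48-h record for DAY 2, and it contradicts 3.1.3 on pre-dose records from the infusion date. No passage in either document corrects this.

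The effect on 48-h infarct volume is small: the DAY 2 row still catches about 96% of scans within 48 h +/-4 h under uniform start times, and about 4% go to DAY 6. The DAY 1 row is the clearer failure for 24-h assessments, since it catches only about 4% of records at 24 h +/-4 h. These shares rest on the start-time assumption. The number of records affected is not given and is probably small, and the direction of any bias is unknown. The plan does not support a conclusion that the ranked endpoints are materially compromised.

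**What to change.** Amend SAP 3.1.2 and Table 5 before unblinding, in one of two ways.

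1. **Realign the rows with 3.1.1.** The 24-h visit becomes analysis Day 2 (window 2 to 2), the 48-h visit has target Day 3 (window 3 to 4), and DAY 6 starts at Day 5. Post-dose records on analysis Day 1, including the post-EVT MRI, keep a row of their own. Under uniform start times this files 91.7% of 24 h +/-4 h records and 95.8% of 48 h +/-4 h scans correctly (Days 3 and 4: 91.7% + 4.2%, rounded).
2. **Window the early records by hours from infusion start** where a time is recorded, as Table 6 already does for vital signs. Limits such as 12 to <36 h for the 24-h visit and 36 to <72 h for the 48-h visit would contain both +/-4 h ranges entirely. They are only an example, and the team should choose its own. Where only a date exists, use the realigned rows.

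In either case, let 3.1.3 govern baseline in place of the Day -1 limit. Add one sentence saying that a scheduled CRF record takes precedence over an unscheduled or early-termination record for the same visit.

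The cost is one table edit, one or two sentences and the matching programming change. No new data are needed.

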Table 1-1: Schedule of Activities for Randomized Participants

Visit/Contact	V1	V2	V3	V4	V5	V6/ End of Trial
Day	Day 0 Baseline	Day 1 Post-EVT	Day 2/or early discharge	Day 6 ¹ or discharge	Day 30 ²	Day 90 ²
Window		(24 h+/-4h)	(48 h+4h)		(±5 d)	(-21 to +7d)
Informed consent	X					
Regained capacity informed consent ³			X	X	X	X
History and physical examination ⁴	X	X	X			
Weight ⁵	X		X			
Vital Signs (BP, HR, Temperature) ⁶	X	X	X			
Chest radiograph	X ¹²	X	X			
Electrocardiogram ⁷	X ¹²	X	X			
Randomization/ Study drug administration	X	X	X			
Continuous telemetry ⁷	X	X	X			
Mortality		X	X	X	X	X
NIHSS ¹³	X	X	X	X	X	X
mRS	X			X	X	X
Barthel Index	X				X	X
EQ-5D-5L						X
Imaging (NCCT & mCTA)	X					
Endovascular Procedure	X					
MRI head ⁸		X	X			X
Laboratory Assessments	X ⁹		X			
Pregnancy test ¹⁰	X					
Blood collection for RNA analysis ¹¹		X	X			X
Blood collection for Plasma Biomarker		X	X			X
AE				Collected to Day 90		
SAE				Collected to Day 90		
Prior medications	X					
Concomitant medications				Collected to Day 90		

1. Visit will occur at Day 6 or hospital discharge if prior to Day 6.
2. At Day 30 and Day 90 it is preferred that participants will return to clinic. If an in-clinic visit is not possible the participant can be contacted by telemedicine (preferred) or by telephone (last option).
3. If the original process involved anyone other than the participant (and if required), site staff will make ongoing efforts until: (1) regained capacity consent is obtained from participant, (2) death, or (3) completion of the Day 90 assessment.
4. Physical exam every 8-12 hours during Day 1 and Day 2.
5. At baseline estimated or actual weight will be collected. If an estimated weight was collected at baseline, actual weight should be collected as soon as feasible and prior to discharge.
6. Vital signs (BP, HR only) will be recorded immediately before and after completion of the study drug infusion, and every 8-12 hours during Day 1 and Day 2, temperature will be collected at baseline only if standard of care.
7. Abnormal electrocardiogram or continuous telemetry result that suggests clinical instability will prompt a formal cardiology consult.
8. MRI head with perfusion imaging within approximately 2h post-EVT on Day 1 and at 48h +/- 4h. MRI head only at 90d.
9. Blood should be drawn at baseline, but results are not required prior to randomization. Results from primary hospital (within 8 hours) are accepted.

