5.2 Exclusion Criteria

- 1) Evidence of a large core of established infarction defined as ASPECTS 0-4.
- 2) Evidence of absence of collateral circulation on qualifying imaging (collateral score of 0 or 1 if mCTA is used or absence of adequate ischemic penumbra in the judgment of the Investigator if CTP is used).
- 3) Any evidence of intracranial hemorrhage or mass lesion on the qualifying imaging.
- 4) Planned use of an endovascular device not having approval or clearance or has been recalled by the relevant regulatory authority.
- 5) Endovascular thrombectomy procedure is completed as defined by the presence of arterial access closure.

- 6) Clinical history, past imaging or clinical judgment suggesting that the intracranial occlusion is chronic or there is suspected intracranial dissection such that there is a predicted lack of success with endovascular intervention.
- 7) Estimated or known weight >130 kg (287 lbs).
- 8) Known pregnant/lactating female.
- 9) Myocardial infarction within 6 months prior to Screening including non-Q wave MI; Diagnosis of congestive heart failure (CHF) with either:
 - a) current clinical signs and symptoms of ventricular dysfunction (e.g., edema, shortness of breath),
 - b) CHF medication adjustment within the prior 30 days or
 - c) ejection fraction (if report available) of 30% or less measured in the 6 months prior to Screening;as either medically documented or reported by patient or another person considered by the Investigator to be reasonably reliable.
- 10) Known renal impairment defined as requiring renal replacement therapy (hemo- or peritoneal dialysis).
- 11) Inability to have MRI imaging (non-MR compatible implants or any other foreseeable reason including claustrophobia)
- 12) Severe or fatal comorbid illness that will prevent improvement or follow up.
- 13) Inability to complete follow-up treatment to Day 90.
- 14) Participation in another clinical trial investigating a drug, medical device, or a medical procedure in the 30 days preceding trial inclusion and throughout the duration of the trial.
- 15) Reported known seizure at time of stroke onset.
- 16) Ischemic stroke within previous 30 days.
- 17) Patients in normal sinus rhythm with a known QTcF > 460 ms at Screening.
- 18) Any other symptom that in the investigator's opinion may complicate or preclude the subject from participating in this trial.

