6.2 Preparation / Handling / Storage / Accountability

Only participants enrolled in the trial may receive study drug and only authorized site staff may supply or administer study drug. Study drug dosing will be carried out by, or under the supervision of, the investigator who is supervising the care of the participant for the planned or ongoing endovascular reperfusion procedure.

As soon as the participant is deemed eligible for the trial, the investigator (or delegate) will log into the central randomization website to receive the assigned bag number.

Dose timing starts at the time of infusion onset. Study drug is intended to be administered as soon as possible after randomization (i.e., <30 minutes) and must be started prior to arterial access closure.

Study drug will be provided in a **Redacted** will contain 375 mL of study drug for single use only.

Redacted**Redacted**

Research site staff will inform the Investigational Pharmacy about local inventory so that the pharmacy can prepare and have correct bags (RNS60 or placebo) on time to study staff.

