The attributes of the main estimand (target of estimation), used for the primary analysis of the highest ranked efficacy endpoint (modified Rankin Scale (mRS) score) are defined below. Although the primary objective of this study is related to safety, analysis of the efficacy endpoints (secondary objectives of the study) will be based on a pre-defined hierarchy and therefore, an estimand is defined.

- The **population** is defined as the intent-to-treat study population (see Section 3.2.3).
- The corresponding **variable** to be obtained for each subject required to address the scientific question is disability based on the mRS score at Day 90. The mRS will be evaluated as a binary outcome (0-2, 3-6).
- The **population level summary** considered in this study is the odds ratio between RNS60 1.0 mL/kg/h and placebo 1.0 mL/kg/h.
- The **treatments** to be compared are RNS60 1.0 mL/kg/h and placebo 1.0 mL/kg/h. The treatments will be compared according to the randomized groups, regardless of the treatment that was actually received. In accordance with the treatment policy principle, all available data will be used in the analysis, regardless of e.g., premature discontinuation of study medication or administration of any concomitant treatment.
- The **intercurrent events** (ICEs) considered as potentially impacting results and/or interpretation are:
 - Premature discontinuation of study treatment
 - Death
 - Coronavirus Disease 2019 (COVID-19) pandemic related events (assessments that were missed due to COVID-19).

For the data that are missing due to premature discontinuation of study treatment, an assumption of Missing At Random (MAR) will be made. Sensitivity analyses will be conducted using an assumption of Missing Not At Random (MNAR). No specific imputation will be done for these missing data, because the likelihood-based analysis approach can manage subjects with incomplete data under the assumption of MAR.

For the data that are missing due to COVID-19, an assumption of MAR will be made for all analyses, both primary and sensitivity analyses.

For the mRS, NIHSS and BI endpoints death is included as part of the scoring, so no imputation of these endpoints is required for subjects who die. Similarly, for the worsening of stroke endpoint, death represents a worsening. For the infarct progression end point, death will be represented by a missing value.

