All participants, investigators, their clinical staff, local laboratories, study personnel, the data management group, and the sponsor staff and delegates will be blinded to the randomization codes and study drug assignment. All study personnel (Contract Research Organization (CRO) and Sponsor and sites) will remain blinded to this data until database lock, at minimum. In the event of emergency unblinding due to participant safety, the Investigator may request unblinding of that participant only. Processes and procedures for unblinding will be accordance with the study protocol, Data Management Plan, Safety Management Plan, and any applicable CRO or Sponsor Standard Operating Procedures.

2.2.3 *Study Drug*

RNS60 is [REDACTED]

[REDACTED] RNS60 has demonstrated exceptional safety in rodent and non-human primate toxicity studies. Additionally, RNS60 has demonstrated significant efficacy in a non-human primate model of acute ischemic stroke without any indications of adverse effects. In all clinical studies to date, RNS60 has been well tolerated. In this study, infusion will begin prior to the completion of the endovascular revascularization procedure (defined as the time of arterial access closure) and complete 48h after the infusion is initiated.

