In addition to the primary time point of each endpoint (as defined below), all other applicable time points will be compared as well and interpreted in an exploratory manner.

In these analyses, testing the combined-dose versus placebo will be done within the statistical models by averaging the results in the two active doses and comparing to placebo. (This is in contrast to performing a separate analysis in which subjects on active dose are treated as a single treatment arm.)

Generalized linear mixed models will be implemented for the analyses of disability based on mRS, infarct volume, NIHSS at 24 hours, worsening of stroke, and Barthel Index. NIHSS will be analyzed on the recorded scale of measurements and the treatment groups' Least Squares (LS) means, corresponding 95% confidence intervals (CIs), and LS mean differences will be reported. Disability based on mRS, worsening of stroke, and Barthel Index are dichotomized endpoints that will be analyzed on the logit scale of measurement. The resulting LS means and confidence intervals will be back-transformed to probabilities, and differences in least squares means will be reported as odds ratios. Infarct volume will be analyzed as log-normally distributed, and descriptive statistics will be geometric means where between-group comparisons will be reported as ratios of geometric means. Covariates baseline NIHSS and ASPECTS binary factors for efficacy analysis will use baseline values from the Electronic Data Caputre.

1. Modified Rankin Scale (mRS) score:

The effect of treatment on global disability at Day 90 will be examined by comparing the proportion of subjects who had disability (Yes or No) between the three treatments (RNS60 1.0 mL/kg/h, RNS60 0.5 mL/kg/h, and placebo 1.0 mL/kg/h) using generalized linear mixed modeling (GLM) using residual pseudo-likelihood with a subject-specific expansion(RSPL) assuming a binary outcome (0-2=0, 3-6=1). Covariates include the Age, baseline NIHSS, and ASPECTS binary factors used for block urn randomization and baseline (pre-morbid) mRS, baseline occlusion location, study site, baseline perfusion status, and log of baseline infarct volume. Treatment, visit day, and interaction of treatment and visit day are included as categorical fixed effects.

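### The mRS, worsening-of-stroke and Barthel models adjust for a baseline infarct volume that is measured after study drug has started

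*SAP*

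**What the plan says.** SAP 3.1.3 gives a general rule, "Baseline is defined as the last measurement prior to start of the study drug infusion", and then departs from it for one variable: "Baseline infarct volume indicates the initial infarct volume as obtained from the first MRI approximately 2 hours post-endovascular thrombectomy on Day 1". The timing agrees with footnote 8 of Protocol Table 1-1: "MRI head with perfusion imaging within approximately 2h post-EVT on Day 1 and at 48h +/- 4h".

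Dosing comes earlier. Protocol 6.2 says that study drug "must be started prior to arterial access closure". SAP 2.2.3 says that "infusion will begin prior to the completion of the endovascular revascularization procedure". Exclusion criterion 5 (Protocol 5.2) removes patients in whom the procedure is already over: "Endovascular thrombectomy procedure is completed as defined by the presence of arterial access closure". SAP 3.3.2 lists a start after closure as a reportable deviation.

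The covariate list for the mRS model in SAP 3.4.2 (1) ends with "study site, baseline perfusion status, and log of baseline infarct volume". The worsening-of-stroke model (3.4.2 (4)) and the Barthel model (3.4.2 (5)) also include the log of this volume, as does the 48-hour infarct-volume model (3.4.2 (2)). The covariate text of the NIHSS model cannot be read in the public SAP, so it is not judged here.

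Protocol 9.3.3 names no such covariate, and SAP 6.4 does not list it among the changes from the Protocol.

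**The concern.** A covariate in a randomized comparison should be fixed before treatment can act on it. This one is not, and it lies on the pathway through which the drug is meant to work: reducing infarct volume is a trial objective and ranks second in the SAP hierarchy, and Protocol 2.1.4 cites smaller infarcts with better neurobehaviour in primates.

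SAP 2.1.3 sets the mRS estimand as an odds ratio by randomized group under treatment policy, where "all available data will be used in the analysis, regardless of e.g., premature discontinuation of study medication". That sentence concerns data after discontinuation and does not mention covariates. But an odds ratio conditional on a post-dose scan does not target the effect of randomized assignment if the drug changes early volume. It approximates the effect not carried by early infarct volume, and it can also pick up bias from unmeasured causes shared by early volume and outcome.

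Setting shared causes aside, if the drug shrinks the early infarct, the ranked odds ratio moves toward 1; if it enlarges it, the odds ratio looks too favourable. Mortality and SAEs are not affected. What is at stake is the ranked efficacy testing and the effect sizes that Protocol 9.3.3 wants for planning the next trial.

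**Working it through.** **Order of events for a patient dosed to plan**

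1. Randomization, with infusion starting within 30 minutes and before arterial access closure (Protocol 6.2).
2. Arterial access closure, which defines the end of EVT.
3. First MRI, within about 2 hours after EVT: the SAP's baseline infarct volume.

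The scan follows EVT and the infusion starts before EVT ends, so the covariate is post-dose however soon the scan is done.

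**Does any planned analysis drop the covariate?**

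- mRS MNAR analysis (SAP 3.4.2 (1), Step 5): refers back to the same model.
- Barthel missing-value analysis (3.4.2 (5)): same approach as its primary analysis.
- Collateral and additional-covariate analyses (3.4.3, 3.4.4.3): only add terms.
- Day 90 mRS 0-2 vs 3-6 counts by arm (3.4.2 (1)) and the Wilcoxon test on mRS 0-6 (3.4.4.1): free of the covariate, but neither is the ranked test.
- Worsening and Barthel: no comparison without it is visible. The SAS code is redacted, so this rests on the text.

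**Illustration of size.** The plan has no figure to reproduce, because no efficacy power calculation was done. The only documentary inputs are a placebo mRS 3-6 rate of about 50% (Protocol 2.1.2), about 33 patients per arm (100 at 1:1:1) and two-sided alpha 0.05. Everything else is assumed.

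Model, with T = 1 for drug, S a standard normal pre-infusion prognostic score, e independent standard normal, V the volume at the scan, r the drug/placebo volume ratio at the scan, and b the log-odds of mRS 3-6 per unit of log V:

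- log V = 1.2 × (0.5 S + 0.866 e) + T × ln r
- logit P(mRS 3-6) = 0.6 S + b log V + [ln 0.5 − b ln r] × T

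The total conditional odds ratio is 0.50 at every r. With log V in the model, the treatment term is ln 0.5 − b ln r, so

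**scan-adjusted OR = 0.50 / r^b**

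For example, at r = 0.67 and b = 0.6: 0.67^0.6 = 0.786, and 0.50 / 0.786 = 0.636.

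| r | b = 0.4 | b = 0.6 | b = 0.9 |
|---|---|---|---|
| 1.0 | 0.50 | 0.50 | 0.50 |
| 0.9 | 0.52 | 0.53 | 0.55 |
| 0.8 | 0.55 | 0.57 | 0.61 |
| 0.67 | 0.59 | 0.64 | 0.72 |

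Simulation with 400,000 per arm agrees with the formula. The row r = 0.67 supposes that the whole of an assumed 48-hour ratio is already on the first scan. At b = 0.6, an odds ratio of about 0.71 needs r of about 0.56 (0.50 / 0.56^0.6 = 0.708).

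Adjusting for S alone gives 0.53 at every r (0.51 to 0.56 across the range of b). Its gap from 0.50 is non-collapsibility, not bias. The crude proportions at b = 0.6 are 50% vs 37%, crude OR 0.58 before rounding, again at every r.

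**Power** at 33 per arm, b = 0.6, single-visit logistic model (6,000 runs, Monte Carlo error about 0.5 points):

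| r | log V in model | log V left out |
|---|---|---|
| 1.0 | 23% | 21-22% |
| 0.9 | 20% | 21-22% |
| 0.8 | 16% | 21-22% |
| 0.67 | 12% | 21-22% |

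The planned model is longitudinal, with site, so only the contrast between columns is informative.

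**Why the infarct-volume model is different.** Protocol 8.1.10 defines growth against the post-thrombectomy scan. With an assumed SD of 1.2 for log volume and 0.5 for growth, a total ratio of 0.67 and none of it yet on the scan, the standard error of the log ratio is 0.123 conditional on the scan and 0.284 adjusted for S only (power 90% vs 29%). Conditioning is right for that question.

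**The case against.** The strongest reply is that this is a disclosed choice. The SAP states the exception openly, no MRI before infusion is scheduled, and early infarct volume is strongly prognostic. Only a small part of the 48-hour infusion may have run by the scan, and the animal results in Protocol 2.1.3 and 2.1.4 report no effect within hours. At a volume ratio of 0.9 the two models barely differ. The unadjusted mRS counts and the Wilcoxon test already give estimates free of the covariate, and infarct volume is also summarized at baseline, which would show an early imbalance if tabulated by arm. Efficacy is secondary and unpowered.

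Much of this stands as a limit on size. So does a technical point: the formula assumes volume is measured without error and shares no unmeasured cause with outcome. Adding measurement error of SD 0.6 or 1.0 log units at r = 0.67, b = 0.6 gives an adjusted odds ratio of about 0.60 or 0.58 rather than 0.64. An unmeasured common cause moves it between about 0.55 and 0.82, depending on sign and strength. The direction of distortion is therefore not guaranteed.

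None of this makes a post-dose variable a valid baseline covariate. Disclosure does not change the estimand, the covariate-free summaries are outside the ranked testing, and there are none for worsening or Barthel. Nor can the sponsor easily call an early effect implausible: Protocol 2.1 describes a therapeutic window of minutes to a few hours.

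**Conclusion.** The concern holds. The timing and the covariate lists are plain in the documents: in patients dosed to plan, the three models adjust for a measurement taken during treatment, and no visible model-based analysis omits it. Confidence in that is high.

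The consequence is conditional. If volume at the scan is unchanged by the drug, nothing is lost. On the assumed values, a true conditional odds ratio of 0.50 would be reported as 0.53 (0.52 to 0.55), 0.57 (0.55 to 0.61) or 0.64 (0.59 to 0.72) at volume ratios of 0.9, 0.8 or 0.67. These figures rest on an assumed effect, coefficient and variance structure in a simplified model, and the real loss could be small. For mRS the harm is partly offset by the unadjusted summaries. It should be fixed, but it does not threaten the primary safety objective.

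**What to change.** 1. In the mRS, worsening and Barthel models, use only covariates fixed before infusion: age, NIHSS, ASPECTS, occlusion location and site, plus pre-morbid mRS (mRS model) or baseline BI (Barthel model). Keep perfusion status only if it is read from imaging acquired before infusion; the SAP does not say which scan supplies it.
2. Move the versions with log post-EVT infarct volume to supportive analyses.
3. Rename the variable post-EVT infarct volume throughout.
4. Leave the infarct-volume model conditioned on the post-EVT scan, and label its result as growth after that scan.

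The cost is SAP wording, shorter covariate lists in three models and one supportive run for each; no new data. If the drug has no early effect on volume (r = 1), leaving the covariate out changes simulated mRS power from 24.6% to 24.2% (b = 0.4), 22.7% to 21.7% (b = 0.6) or 21.0% to 19.0% (b = 0.9), a loss of about 0 to 2 points. At r = 0.67 the same change raises it from 15.5% to 22.4%, 11.9% to 21.4% and 8.0% to 18.3%.
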